### Revision History:

Title	Scope	Key words	Date
CIP 2-0 Amendment 1	ALL sites	Change of the exclusion criterion No. 2 (substantial)	20-Apr-2022

## 1 LIST OF ABBREVIATIONS

ADE	Adverse Device Effect
AE	Adverse Event
ASADE	Anticipated Adverse Device Effect
BP	Blood Pressure
CA	Competent Authority
CDMS	Clinical Data Management System
CE	CE mark, a stylized "CE" (Conformité Européenne) placed on products to signify conformance with European Union regulations
CI	Coordinating Investigator
CIP	Clinical Investigation Plan
CIR	Clinical Investigation Report
CLS	Closed Loop Stimulation
CRF	Case Report Form
DD	Device Deficiency
eTMF	electronic Trial Master File
EC	Ethics Committee
FU	Follow-up visit
HR	Heart rate
HUTT	Head-Up Tilt Test
ICF	Informed Consent Form
ICH	International Conference on Harmonisation of Technical Requirements for Registration of Pharmaceuticals for Human Use ( www.ich.org )
IEGM	Intracardiac Electrocardiogram
IRB	Institutional Review Board
IFU	Instructions For Use (user manual)
iMedNet	Web-based electronic data entry (EDC) system for clinical trials provided by MedNet Solutions Inc.
ISO14155	International Organization for Standardization, norm no. 14155
SADE	Serious Adverse Device Effect
SAE	Serious Adverse Event
SAP	Statistical Analysis Plan
SAS	Statistics and Analysis Software produced by SAS Institute Inc. www.sas.com )
SDS	Source Data Sheet
SV	Stroke Volume
TPR	Total Peripheral Resistance

## 2 SYNOPSIS

Title	BIO Sync-HUTT
Patient population	The study will select patients with reflex syncope and positive cardioinhibitory response to Head-Up Tilt Test (HUTT) who had already participated in the BIOSync study.
Design	Prospective, non-randomized, multi-center, observational, acute study.
Investigational device(s)	The closed-loop stimulation (CLS) algorithm implemented in current dual-chamber pacemakers manufactured by BIOTRONIK.
Objectives	To provide standardized, complete and quality controlled data sets with parameters that describe hemodynamic changes and their timing with respect to CLS pacing activation during reflex syncope induced by HUTT.
Data of interest	
a) Heart rate, blood pressure, stroke volume, and peripheral resistance at the following time-points during HUTT:
 
 
• Time of maximum spontaneous heart rate (end of phase 1/beginning phase 2 of the reflex);
 
• Time of pacing onset;
 
• Time of recovery of spontaneous rhythm after pacing (end of recovery period);
 
• time of syncope (i.e. loss of consciousness) during HUTT (also assessed by video recording if available at investigational site);
 
• time of tilt-down (supine patient position just after tilt-down);
 
 
b) Above-mentioned times of interest expressed as intervals (MM:SS) from the start of the HUTT
 
c) Duration of the recovery phase (interval from maximum pacing rate to basic rate or spontaneous rhythm expressed in MM:SS from the start of the HUTT)
 
d) Slopes in heart rate (bpm per sec) and systolic blood pressure (mmHg per sec) during the recovery phase

Title	BIO Sync-HUTT
Inclusion criteria	
 
• Ability to understand the nature of the study.
 
• Willingness to provide written informed consent.
 
• Patients undergoing HUTT for monitoring of syncope, therapy adjustment, training or other medical reasons during ordinary follow-up, irrespective of study participation.
 
• Patients who participated in the BIOSync study*.
 
• Patients with a dual-chamber pacing system equipped with the CLS algorithm.
 
 
* If needed, inclusion of other patients who did not participate in the BIOSync study will be considered to complete study cohort, provided that they have already a CLS pacemaker system and fulfill the same inclusion/exclusion criteria of the BIOSync study.

Exclusion criteria	
 
• Pregnant or breast feeding women.
 
• Age less than 40 years.
 
• Patients who after the BIOSync study participation have developed the following: 
 
- Any indication to pacemaker different from reflex syncope with positive HUTT response; or
 
- Any classified indication to implantable defibrillator, cardiac resynchronization therapy according to current guidelines; or
 
- Any cardiac dysfunctions likely leading to loss of consciousness
 
 
 

Study duration	~ Q1 2022 – Q3 2023 (~ 19 months)
Sample size	A total of 20 patients will be included in the study.
Number of investigational sites	The study will be conducted in at least 2 sites.
Number of follow-ups per patient	This is an acute study. Investigational procedures will be conducted at any HUTT performed according to routine clinical practice. Patients who undergo HUTT during ordinary follow-up visits irrespective of study participation, are eligible. The study has no additional follow-ups after HUTT execution.
Coordinating investigator	
Boards (if applicable)	None

Title	BIO Sync-HUTT
Sponsor	BIOTRONIK SE & Co. KG Center for Clinical Research [name] [name]

In this investigational study the term 'patient' is identical with the term 'subject' as defined in ISO 14155, because all study participants are patients treated by physicians at the investigational sites.

### 3 INTRODUCTION

The 2021 European Society of Cardiology guidelines recommend cardiac pacing in patients aged >40 years with tilt-induced asystolic reflex syncope (class I, level of evidence A). (1) The recommendation relies on recent results from the multicentre, randomised, double-blinded, parallel-design BIOSync trial. (2) The BIOSync study provided evidence of benefit of dual-chamber pacing in patients with tilt-induced reflex syncope and confirmed the role of Head-up Tilt Table (HUTT) test as a diagnostic method for cardiac pacing in reflex syncope. The study randomised patients aged  $\geq 40$  years with frequent reflex syncope and VASIS 2B cardio-inhibitory response to HUTT to receive either an active or an inactive dual-chamber pacemaker with the CLS pacing mode. The rationale for pacing with CLS in cardioinhibitory reflex syncope was recently reviewed by Tomaino et al. (3) CLS is able to measure changes in intracardiac impedance during the systolic phase of each cardiac cycle which are strictly correlated to the increased heart rate and right ventricular contraction speed which are usually present during the pre-syncope phase of the reflex. It was hypothesized that an early onset of CLS pacing may be triggered by the compensatory increase in heart rate to counteract vasodilation and pressure drop during the pre-syncope phase of the reflex. The BIOSync study showed a 77% reduced risk of syncope in the DDD-CLS group as compared to pacing off. The design of the BIOSync study did not allow to assess the specific effect that CLS adds to dual-chamber pacing. Despite DDD-CLS pacing, 22% of patients had syncopal recurrence in 2 years. Further investigations are therefore needed in order to reduce this failure rate. Indeed, it is still unclear whether syncopal recurrences should be ascribed to dominant vasodilation or if the CLS programming/functioning needs optimization to more adequately sustain cardiac output during reflex in these specific cases. (3) The purpose of this study is to explore changes in hemodynamic parameters during HUTT and their timing with respect to CLS pacing activation. This study may add knowledge to better understand the mechanisms underlying recurrent syncopal events and optimal pacing programming.

## 4 DEVICE(S) USED IN THE STUDY

The following devices, tools and accessories will be used during the study:

- the CLS algorithm (as investigational device in this investigation according to, ISO14155) implemented in current dual-chamber pacemakers manufactured by:

BIOTRONIK SE & Co. KG  
[name]  
[name]  
Germany  
www.biotronik.com

- RENAMIC programmers or later models;
- Any external monitor capable of measuring continuously patient's hemodynamics (e.g. Task Force Monitor);
- Standard equipment needed for the HUTT execution.

Such devices must be available at the investigational sites before study participation and will not be provided by the Sponsor.

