### **7.2 Objectives (Endpoints)**

This study will provide standardized, complete and quality controlled data sets with parameters that describe hemodynamic changes and their timing with respect to CLS pacing activation during reflex syncope induced by HUTT.

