9.2.3 Head-up tilt test

The HUTT will be performed according to the Italian protocol (9) and patient's hemodynamics will be continuously monitored during the entire test. Specifically, an external monitor will be used for continuous measurement and recording of systolic and diastolic BP, HR, SV, and TPR.

Prior to the start of the HUTT, a trained member of the study team will prepare the patient and set up the equipment needed for the test as follows:

- patient shall be supine on the tilt table and secured to it with the BP sensor cuff of the external monitor on his/her finger. Hand wearing the pressure sensor shall be placed on the chest at about 10 cm from heart and held in this position throughout the test;
- ECG leads shall be placed on patient’s chest and a BP cuff on his/her arm;
- If used, a high-definition camera may be placed to contemporarily pick up both patient and the external monitor positioned close to the tilt table.

**Note: video recordings of the entire test shall not be provided to the Sponsor and will be destroyed immediately after the examination. The investigator will assess the time of symptoms onset and will report it in the CRF.**

After 10 minutes in supine position, the patients will be tilted to 70° using an electronically operating tilt-table with a footboard.

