## **9.5 Possible influencing factors on outcome or interpretation of results**

No factors that could influence the outcome or interpretation of the results are known at time of protocol drafting.

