descriptive	CVSBPAPC	Systolic BP at time of recovery of basic pacing rate or spontaneous rhythm after pacing (end of recovery period) [mmHg]	Scale	n.a.	
descriptive	CVDBPAPC	Diastolic BP at time of recovery of basic pacing rate or spontaneous rhythm after pacing (end of recovery period) [mmHg]	Scale	n.a.	
descriptive	CVSBPHU	Systolic BP at time of syncope during HUTT [mmHg]	Scale	n.a.	
descriptive	CVDBPHU	Diastolic BP at time of syncope during HUTT [mmHg]	Scale	n.a.	
descriptive	CVSBPAHU	Systolic BP at time of tilt-down (supine patient position just after tilt-down) [mmHg]	Scale	n.a.	
descriptive	CVDBPAHU	Diastolic BP at time of tilt-down (supine patient position just after tilt-down) [mmHg]	Scale	n.a.	

FOR-137-059-C / SOP-137-060.020 / CRQ200005199

	descriptive	CVSVHUST	SV at HUTT start [ml]	Scale	n.a.
	descriptive	CVSVMHRT	SV at time of maximum spontaneous heart rate (end of phase 1/beginning phase 2 of the reflex) [ml]	Scale	n.a.
	descriptive	CVSVPC	SV at time of pacing onset/maximum pacing rate [ml]	Scale	n.a.
	descriptive	CVSVAPC	SV at time of recovery of basic pacing rate or spontaneous rhythm after pacing (end of recovery period) [ml]	Scale	n.a.
	descriptive	CVSVHU	SV at time of syncope during HUTT [ml]	Scale	n.a.
	descriptive	CVSVAHU	SV at time of tilt-down (supine patient position just after tilt-down) [ml]	Scale	n.a.
	descriptive	CVTPRHUS	TPR at HUTT start [dyn·s/cm ⁵]	Scale	n.a.
	descriptive	CVTPRMHR	TPR at time of maximum spontaneous heart rate (end of phase 1/beginning phase 2 of the reflex) [dyn·s/cm ⁵]	Scale	n.a.
	descriptive	CVTPRPC	TPR at time of pacing onset/maximum pacing rate [dyn·s/cm ⁵]	Scale	n.a.
	descriptive	CVTPRAPC	TPR at time of recovery of basic pacing rate or spontaneous rhythm after pacing (end of recovery period) [dyn·s/cm ⁵]	Scale	n.a.
	descriptive	CVTPRHU	TPR at time of syncope during HUTT [dyn·s/cm ⁵]	Scale	n.a.
	descriptive	CVTPRAHU	TPR at time of tilt-down (supine patient position just after tilt-down) [dyn·s/cm ⁵]	Scale	n.a.
Termination	Case listing	COSUM	General Comments	Text	n.a.
Data_SAR	descriptive	SLOPE_HR_HUTT_SAR	Slope in heart rate (bpm per sec) during the recovery phase	Scale	n.a.
Data_SAR	descriptive	SLOPE_SBP_HUTT_SAR	Slope in systolic blood pressure (mmHg per sec) during the recovery phase	Scale	n.a.

FOR-137-059-C / SOP-137-060.020 / CRQ200005199

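### Monitor choice is left to each site, yet the SAP summarises stroke volume and peripheral resistance only as pooled absolute values, with no monitor variable and no within-patient change

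*Protocol*

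**What the plan says.** The objective in Protocol 7.2 is to provide "standardized, complete and quality controlled data sets with parameters that describe hemodynamic changes" and their timing relative to CLS pacing.

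**Instrument.** Protocol 4 allows "Any external monitor capable of measuring continuously" the patient's haemodynamics, naming one product only as an example. It adds: "Such devices must be available at the investigational sites before study participation and will not be provided by the Sponsor". Protocol 9.2.3 narrows this somewhat: "an external monitor will be used for continuous measurement and recording of systolic and diastolic BP, HR, SV, and TPR". It calls for the "BP sensor cuff of the external monitor on his/her finger" and a fixed hand position. It gives no model, SV method, calibration or averaging window. At least two sites take part (Protocol 8.1.7).

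**Analysis.** SAP 10.2 lists six SV rows and six TPR rows: HUTT start, maximum spontaneous heart rate, pacing onset, end of recovery, syncope and tilt-down. A typical label is "SV at time of pacing onset/maximum pacing rate [ml". Each is described in absolute units over one pooled set (SAP chapter 8). The only derived haemodynamic variables are the slopes of heart rate and systolic pressure. The SAP tables contain no monitor variable, and SAP 12.14 marks exploratory and sensitivity analysis as not applicable.

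**Influencing factors.** Protocol 9.5 states: "No factors that could influence the outcome or interpretation of the results are known at time of protocol drafting".

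**The concern.** The introduction to the protocol asks whether recurrences reflect dominant vasodilation or pacing that does not adequately sustain cardiac output. TPR and SV are the collected variables that bear most directly on that question. They also depend on how the monitor derives them. The SAP's TPR unit, dyn·s/cm⁵, is a pressure divided by a flow, so a monitor that reads SV high would be expected to read TPR low.

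With 20 patients and perhaps two sites, monitor and site could be nearly the same factor. If the monitors disagree, the pooled mean is a blend of two scales and the pooled SD includes the disagreement. An offset could also pass for a difference in SV or vasodilation wherever the groups being read against each other have a different monitor mix. The planned tables would not show the reader that this had happened.

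**Working it through.** The plan gives no SD, expected SV or TPR, or between-monitor difference, and Protocol 12.5 states that the sample size rests on no specific calculation. There is no planned figure to reproduce, so everything below is illustrative.

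**Inputs from the documents:** n = 20 (Protocol 12.5); at least 15 fully analysable (8.1.6); at least 2 sites (8.1.7); t-based confidence intervals (SAP 12.3); 5% two-sided threshold (SAP 12.4).

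**Assumptions:** two monitors, A and B, with 10 patients each; true SV mean 70 ml and SD 15 ml; monitor A reads true; monitor B reads k times true, with k = 1.1, 1.2 or 1.3.

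**1. Pooled mean and SD under a scale offset**

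Mean = 70(1 + k)/2.

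SD = √{[15² + (15k)²]/2 + [70(k − 1)/2]²}.

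- k = 1.1: mean 73.5 ml; SD = √(248.6 + 12.25) = 16.2 ml
- k = 1.2: mean 77.0 ml; SD = √(274.5 + 49) = 18.0 ml
- k = 1.3: mean 80.5 ml; SD = √(302.6 + 110.25) = 20.3 ml

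If the offset were instead additive (d = 7, 14 or 21 ml), SD = √[15² + (d/2)²] = 15.4, 16.6 or 18.3 ml. If the monitor computes TPR from its own SV, TPR on monitor B is multiplied by 1/k, which is 9%, 17% or 23% lower.

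**2. Comparison with the precision available**

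The 95% CI half-width is t(0.975, n − 1)/√n, which is 0.47 SD at n = 20 and 0.55 SD at n = 15. At n = 20 the three scale cases give half-widths of 0.468 × 16.2, 18.0 and 20.3, or about 7.6, 8.4 and 9.5 ml. The mean shifts are 3.5, 7.0 and 10.5 ml.

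**3. Reading across rows**

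Only patients who faint contribute to the syncope rows. With a 50:50 monitor mix at HUTT start and an additive offset d, the apparent change with no true change is (share of the syncope patients on B − 0.5) × d:

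- 4 of 8 on B: 0
- 6 of 8 on B: 0.25d
- 8 of 8 on B: 0.5d

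**4. Optional subgroup comparison**

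This is a 10 v 10 two-sided t-test at 5% with no true difference, 40,000 simulated runs, and an additive offset in SD units. The assumed 7, 14 and 21 ml correspond to 7/15, 14/15 and 21/15 = 0.47, 0.93 and 1.4 SD.

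| Patients on B, group 1 / group 2 | 0.5 SD | 1.0 SD | 1.5 SD |
|---|---|---|---|
| 5 / 5 | 4.5% | 2.8% | 1.4% |
| 7 / 3 | 6.2% | 9.7% | 12.8% |
| 8 / 2 | 9.2% | 19.6% | 34.1% |
| 10 / 0 | 18.5% | 56.3% | 88.5% |

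With a balanced mix there is no bias and the test is conservative. The excess arises only from imbalance.

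**5. What within-patient change does**

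Take an assumed fall in SV from 70 to 40 ml.

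- Additive offset of 7 ml: the absolute change is 47 − 77 = −30 ml, as without the offset. Percent change moves from −42.9% to −30/77 = −39.0%.
- Scale factor 1.1: the absolute change is 44 − 77 = −33 ml. Percent change stays at −42.9%. For TPR, a factor of 1/k likewise leaves percent change unaltered.

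Absolute change removes an additive offset and percent change removes a scale factor. Since the form is unknown, both are needed.

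**The case against.** The strongest reply is that nothing shows a problem exists. The documents do not say that sites use different monitors or that such monitors disagree, and every magnitude above is assumed. Section 9.2.3 does restrict the sensor, the hand position and the required outputs. This stands: the offset could be zero.

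A reader might infer that planned contrasts are biased. The SAP plans none for SV or TPR. SAP 12.4 says there are no pre-specified hypotheses, and Protocol 12.8 mentions subgroup comparisons only as possibilities. A comparison of patients who do and do not faint on the tilt table appears nowhere.

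A reader might also infer that the monitor could never be identified. That goes too far. The patient ID contains a clinic number (Protocol 13.4), so a split by site is possible from existing data. Protocol 4.2 says all medical devices are tracked by serial number, although section 16 specifies CRF recording only for the implanted pacing systems. Neither item reaches a planned output, and a clinic number does not reveal the SV method or a change of monitor within a site.

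SAP 12.7 and 12.9 allow the SAP to be updated if bias becomes evident. That safeguard works poorly when the likely source is not among the listed variables.

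Finally, the tilt test is routine care with the site's own equipment. Imposing one model could exclude one of as few as two sites, and dropping the pooled absolute values would remove data of interest named in Protocol 8.1.3. Both objections stand and limit the remedy.

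**Conclusion.** The point holds as a gap in recording and presentation. The protocol leaves the instrument open while promising standardized data. The SAP then reports SV and TPR only in the form most exposed to an instrument offset, although the introduction gives the purpose as exploring changes in haemodynamic parameters.

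The documents do not establish that an offset exists. If one does, and it is a 10% to 30% scale difference with patients split 10:10, the pooled SV SD rises from 15 ml to about 16.2 to 20.3 ml. The pooled mean moves by 3.5 to 10.5 ml, compared with a CI half-width of about 7.6 to 9.5 ml. Bias in subgroup comparisons or in reading across rows further requires that the monitor mix differ.

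The study is exploratory with no confirmatory test, so the consequence is for interpretation and not for error control. Times, heart rate and the two slopes are outside this argument. The change is worth making because it costs little and an unrecorded SV method may be hard to recover later.

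**What to change.** - **HUTT CRF:** record monitor model and SV method for each patient.
- **SAP 10.2:** keep the pooled absolute SV and TPR rows. Add each patient's absolute and percent change from HUTT start (CVSVHUST and CVTPRHUS, already collected) at each of the five later time points. Because each change is computed within a patient, the syncope rows then compare fainters with their own start values.
- **SAP 10.2, if more than one model is used:** also show SV and TPR by monitor. If the model is missing, split by site using the clinic number in the patient ID.
- **Protocol 9.5:** name the monitor and its SV method as a possible influencing factor.

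The cost is one small addition to the CRF, extra table rows (2 variables × 5 time points × 2 forms of change = 20) and a wording change. Columns by monitor will be small, especially at syncope, and should be read descriptively. A single mandatory model is not needed, and the pooled absolute values should not be removed.

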### 4.1 Model name including software version and accessories

All models of current dual-chamber pacemakers manufactured by BIOTRONIK implementing the CLS algorithm may be included in the study. Devices are used along with any CE-marked leads. A detailed description of the pacing systems is reported in their user manual.

### 4.2 Description of traceability

All medical devices used in the study will be tracked by serial numbers.

### 4.3 Intended purpose of the device(s) in the study

All above-mentioned medical devices are CE-certified and will be used within their intended use and according to their user manual.

### 4.4 Intended patient population and indications

Pacemakers included in this study are used for all bradycardia arrhythmia indications to improve patients' symptoms that can be clinically manifested and compensate bradycardia by atrial, ventricular or Atrio-Ventricular sequential pacing.

The intended study population consists of patients who have indication for the pacemaker therapy according to the current European guidelines. (1) BIOTRONIK pacemakers equipped with CLS are therefore used within their indication.

### 4.5 Description of the CLS algorithm

The CLS algorithm was developed to provide a physiologic pacing rate modulation in response to metabolic demand and it is based on an analysis of the right ventricle unipolar impedance trend during systole. Impedance trend is obtained by sampling with high frequency subthreshold pulse train: an increase of the impedance trend slope, with respect to a (rest) reference, is an indication of an increased metabolic demand and it is used to adapt heart rate accordingly. In particular, impedance changes depend on the amount of blood and myocardial tissue in the volume surrounding the tip of the right ventricular lead. During contraction, blood ejection causes tighter electrode contact with myocardial tissue (involving a larger proportion of tissue relative to blood volume), leading to a progressive impedance increase towards late systole (3). CLS automatically increases pacing rate in response to detected changes in myocardial contractility. CLS functioning actively interacts with the autonomic regulation

process of cardiac output, occurring under several conditions of everyday life, not limited to exercise. (4)

#### **4.6 Summary of training and experience needed**

All investigators must dispose of adequate research training and experience. Training on ISO 14155 and/or several years of experience in conducting clinical trials are generally required.

In addition to having basic medical knowledge, investigators must be thoroughly familiar with cardiac pacing and conduction of HUTT Investigators will be trained on the study procedures.

